### *Section 2 - Audiological test and hearing aid fitting*

Each subject will undergo a routine audiological examination. First an audiogram will be completed. The subject will hear a series of acoustic beeps. The subject's task is to indicate when he or she heard a beep. From this test we can determine the softest sounds that the subject can hear. This will be completed using an audiometer (sound presentation device) and earphones. The earphones will be attached to the subject. Each subject will be fitted for testing with hearing aids or a computer based hearing aid simulator. Tympanometry, a routine audiological test, will be completed.

### *Section 3 - Detection of Acoustic Information*

We will measure the ability of the subjects to detect small changes in the frequency of the signal. Via a touchscreen, the subject will indicate when he or she heard a change in the signal, from which a threshold is estimated. This measure is related to the perception of speech.

### *Section 4 - Speech Recognition*

Speech sounds will be presented at a variety of levels. The subject will repeat back the speech sounds that they heard and their spoken response will be scored.

#### ***Test Time:***

The audiological test and hearing aid fitting is anticipated to take 1 hour to complete. Section two is anticipated to take approximately 3 hours and section three approximately 2 hours. Participants with NH require less time; they are not fit with hearing aids and undergo fewer conditions. In addition to hearing status, the duration will depend on how quickly each subject completes the study and on whether a current audiological test can be used, thereby saving time. Consequently, we anticipate the study will take approximately 3-6

hours per subject. Generally subjects complete the study in 2-3 sessions scheduled over the course of a couple weeks.

***Recruitment:***

Recruitment will occur at the Barkley Speech, Language, and Hearing Clinic, Lincoln and surrounding community facilities that provide audiological or ear nose throat services, and through organizations with older individuals (e.g. OLLI at UNL). Participation will take place at the amplification and perception laboratory.

**Statistical Analysis:**

We plan to enroll 20 subjects with normal hearing and 40 subjects with sensorineural hearing loss (per experiment). While we plan to recruit the same subjects for each experiment, additional subjects will be recruited as needed. Additional subjects will be recruited for pilot testing and to account for attrition. We expect an effect size of 0.37 ( $np2$ ) or greater. Using G\*Power (v3.1) we estimated sample sizes necessary to detect an effect size of over 0.23 (power = 80%,  $\alpha = 0.05$ ). For Aim 1, planned comparisons to examine the effect of prescriptive procedure, compression speed, and number of compression channels on the sharpness of tuning measured will be conducted using an ANOVA or, if we find that the assumptions of the ANOVA to be violated, a linear mixed effect model. For Aim 2, planned comparisons to examine the effect of dynamic range of hearing (small, large) and tuning status (poor tuning, sharp tuning) on proportion correct will be conducted using an ANOVA or, if we find that the assumptions of the ANOVA to be violated, a linear mixed effect model. While results are not expected to differ by sex, differences by sex will be analyzed for all experiments. Other variables, such as age, degree of hearing loss, and working memory likely play a role in spectral resolution and speech recognition and will be considered as variables in our statistical models.

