## **Significance/Purpose:**

Adults with hearing loss are more vulnerable to interference from background noise than adults with normal hearing. Despite the fact that the ability to extract speech information imbedded in background noise requires decoding differences in level across frequency (spectral information), few studies have addressed the extent to which we can provide spectral information to listeners with hearing loss. This fundamental gap in our knowledge prevents us from effectively addressing the systemic effects of hearing loss on communication, income, and ability to socialize with others. This work is a new application of established methods of characterizing spectral resolution to that of the most common device for rehabilitation of hearing loss—hearing-aid amplification. The proposed experiments will examine the degree to which access to spectral information can be restored to adults with hearing loss and the feasibility of utilizing this information to decrease interference from background noise. Aim 1 will delineate the impact of hearing-aid amplification on spectral decoding. Technology options that must be set by the clinician or hearing-aid manufacturer will be examined, including the frequency-specific gain, compressor speed, and number of compression channels. The proposed experiments will test the hypothesis that restoration of the lost dynamic range of hearing can support the encoding of spectral information. It is also hypothesized that the combination of technology options that best restore access to spectral information will differ across individuals and that these differences across individuals can be partially accounted for by an estimate of outer hair cell function. Aim 2 will determine the extent to which restoring access to spectral information supports speech recognition in background noise, under the guiding hypothesis that improving spectral resolution increases speech understanding. If it can be demonstrated that measures of spectral resolution with the provision of amplification are useful at delineating those who stand to benefit from different technology options, the knowledge gained could then be applied to the clinic to allow for clinicians to more successfully choose among different rehabilitation options.

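### The plan has no rule for listeners with incomplete conditions, and its ANOVA-first order could drop their partial data; the mixed model it already names should be primary for both aims.

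*Combined protocol and SAP*

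**What the plan says.** The Statistical Analysis section sets the target: "We plan to enroll 20 subjects with normal hearing and 40 subjects with sensorineural hearing loss (per experiment"). On continuity between experiments it says "While we plan to recruit the same subjects for each experiment, additional subjects will be recruited as needed", and on dropout "Additional subjects will be recruited for pilot testing and to account for attrition". No dropout rate, size of top-up or replacement rule is given.

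Aim 1 consists of "planned comparisons to examine the effect of prescriptive procedure, compression speed, and number of compression channels on the sharpness of tuning". Aim 2 compares proportion correct by dynamic range and tuning status. Both aims carry the same analysis wording: the comparisons "will be conducted using an ANOVA or, if we find that the assumptions of the ANOVA to be violated, a linear mixed effect model".

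Under Test Time, a subject needs about 3-6 hours, and "Generally subjects complete the study in 2-3 sessions scheduled over the course of a couple weeks". The same paragraph says normal-hearing participants have fewer conditions, which implies several for those with hearing loss.

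The document does not define an analysis set or a rule for incomplete listeners. It does not say whether the ANOVA is repeated-measures, or which settings are tested at which visit.

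**The concern.** Several hours of testing over more than one visit make partial records foreseeable, and the plan itself expects attrition. A standard repeated-measures ANOVA needs every cell from every listener, so one missing condition removes the whole person. A likelihood-based mixed model can use the conditions that were completed. The plan names that model but places it behind a condition about ANOVA assumptions, which in ordinary usage means the distribution and covariance of the scores. Incomplete data are not mentioned.

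New recruits replace numbers, not the kind of listener who left. The Significance/Purpose section hypothesises that "the combination of technology options that best restore access to spectral information will differ across individuals", so the average setting effect among those who finish need not equal the average among all who enrolled. At stake are the average setting effects in Aim 1 and, where its factors vary within a listener, the Aim 2 contrasts.

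**Working it through.** **1. What extra recruitment repairs.** The plan gives effect size 0.23, power 80%, alpha 0.05 and 40 listeners with hearing loss. It does not give the effect-size metric, number of levels or within-listener correlation. One standard reading reproduces 40: Cohen's f = 0.23, one group, m = 2 repeated measurements, correlation ρ = 0.5.

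λ = f²·N·m/(1−ρ) = 0.0529 × 40 × 2/0.5 = 8.464 on 1 and 39 df, power 81.0%.

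Other readings give other numbers (28 with four levels at ρ = 0.5; 30 if 0.23 is partial eta squared with two levels), so 40 is neither confirmed nor disputed. Under the first reading, with assumed loss and no top-up:

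| Assumed loss | Left of 40 | λ | Power | Enrol for 40 completers |
|---|---|---|---|---|
| 5% | 38 | 8.04 | 78.9% | 40/0.95 → 43 |
| 10% | 36 | 7.62 | 76.5% | 40/0.90 → 45 |
| 20% | 32 | 6.77 | 71.3% | 40/0.80 = 50 |

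Top-up therefore deals with power. What remains is possible bias.

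**2. Bias when setting is aligned with session (all inputs assumed).** Session 1: y1 = u + e1. Session 2: y2 = u + 0.5 + b + e2. Listener level u has SD 1, each e has SD 0.5, and b = s·u plus noise of SD 0.5. The true setting effect is 0.50. Recruitment continues to 40 completers.

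- *Dropout unrelated to score:* completers average 0.499-0.506, so there is no bias.
- *Dropout more likely with a poor y1* (logistic, slope 1, probability 10% or 20% at the average score): Var(y1) = 1 + 0.25 = 1.25, so E(e1 | y1) = 0.25/1.25·y1 = 0.2·y1 and E(b | y1) = s·(1/1.25)·y1 = 0.8s·y1.

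Hence bias = (0.8s − 0.2) × M, where M is the completers' mean y1. Averaging y1 over its normal distribution, weighted by the probability of staying, gives M = 0.153 (10%) or 0.254 (20%).

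| s | Bias by formula (10%, 20%) | Completers' mean by simulation, 4000 runs |
|---|---|---|
| 0 | −0.031, −0.051 | 0.467, 0.453 |
| +0.3 | +0.006, +0.010 | 0.505, 0.509 |
| −0.3 | −0.067, −0.112 | not simulated |

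The sign changes at s = 0.2/0.8 = 0.25. The standard error at s = ±0.3 is √[(0.09 + 0.25 + 0.25 + 0.25)/40] = √(0.84/40) = 0.145, so the largest bias is 0.112/0.145 = 0.77 of a standard error. Keeping the session-1 data of those who left gave 0.497-0.504 in the simulated score-related cases.

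**3. Bias with four settings, two per visit (all inputs assumed).** Effect 0.5, SD of the effect across listeners 0.5, residual SD 0.4, 60% dropout among listeners whose visit-1 mean is below −0.9 or −0.5, recruitment to 40 completers, standard error about 0.10.

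| Correlation of listener level with setting effect | Completers' bias |
|---|---|
| +0.3 to +0.5 | +0.028 to +0.080, depending on layout |
| 0, effect coded from a baseline setting | about +0.015 to +0.025 |
| 0, effect coded as plus or minus half around the listener's average | −0.002 |
| −0.3 to −0.5, plus-or-minus-half coding | −0.028 to −0.062 |

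The largest is 0.080/0.10 = 0.8 of a standard error. A maximum-likelihood analysis of all observed data had bias between −0.004 and +0.011, with a standard error of 0.098 against 0.102-0.103 for completers.

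**The case against.** A reader might infer that the plan discards partial data, that its setting effects come from completers only, and that these effects are overstated. The documents support none of the three.

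- They do not mention listwise deletion or a repeated-measures ANOVA. An analyst could also treat incomplete cells as failing the ANOVA's requirements and move to the mixed model. The plan is silent, not committed to dropping data.
- Recruiting to account for attrition may mean over-enrolment rather than substitution.
- Settings are not allocated to visits, and the aims are analysed separately. A listener who finishes all Aim 1 conditions and leaves before speech testing could still count in Aim 1.
- Overstatement needs a positive link between overall performance and setting effect. The plan hypothesises that the best settings vary between listeners, not that better performers gain more. Other assumptions reverse the sign.
- The illustrations do not carry over to Aim 2, where the plan does not say which factors vary within a listener.
- The remedy can be over-specified. If three Aim 1 factors were fully crossed at two levels (not stated), there would be 8 conditions, and an unstructured covariance would need 8 × 9/2 = 36 parameters from about 40 listeners.

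All of this stands, and it limits the point to a gap with a foreseeable risk. It does not fill the gap: nothing says what happens to a listener with some conditions missing, and the wording does not clearly lead to the method that would use the data.

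**Conclusion.** The point holds as a gap in the plan, not as a demonstrated bias. Recruitment is the only stated response to attrition, and incomplete data are not a stated route to the mixed model. If the ANOVA is run in its standard repeated-measures form, which the several conditions per listener make likely, anyone who leaves partway through an aim's conditions drops out of that aim's analysis.

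Bias follows only if leaving is related to performance. If it is unrelated, only precision suffers, and top-up restores that. The documents determine neither size nor direction. In the illustrations the bias ran from −0.112 to +0.080 on a true effect of 0.50, below one standard error throughout. Those figures rest on assumed dropout rates, variances and correlations. The change is worth making because it is cheap and uses a model the plan already names.

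**What to change.** In the Statistical Analysis section:

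- Make the likelihood-based linear mixed model the primary analysis for both aims, not the fallback.
- Define the analysis set as every listener with at least one scored condition for that aim.
- Include a listener random intercept and, where the number of conditions allows, random slopes for the within-listener factors. Do not require a fully unstructured covariance if there are many conditions.
- Retain data from listeners who withdraw, and count later recruits as additional listeners rather than substitutes.
- Report the complete-case ANOVA as a sensitivity analysis, with the number leaving after each session.
- State the expected dropout and which factors vary within a listener.

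The cost is revised wording and slightly more modelling work, with no extra listeners or visits. The model relies on dropout being explained by the observed scores (missing at random), a weaker assumption than the complete-case analysis needs.

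### Does the unlabelled effect size of 0.23 in the power statement leave the 40 listeners with hearing loss unsupported?

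*Combined protocol and SAP*

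**What the plan says.** All the sizing information is in the Statistical Analysis section of the combined protocol and SAP. Enrolment is given first: "We plan to enroll 20 subjects with normal hearing and 40 subjects with sensorineural hearing loss (per experiment"). Then comes the anticipated effect, "We expect an effect size of 0.37", with the label np2 in brackets and the words that it may be greater. The next sentence reports the power work: "we estimated sample sizes necessary to detect an effect size of over 0.23", with 80% power and alpha 0.05, and with no scale attached to 0.23.

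ANOVA, or a linear mixed model if its assumptions fail, is named afterwards as the analysis for each aim. Aim 1 has "planned comparisons to examine the effect of prescriptive procedure, compression speed, and number of compression channels on the sharpness of tuning". Aim 2 crosses dynamic range (small, large) with tuning status (poor, sharp). Neither aim is tied explicitly to the G*Power run. Under Test Time, the protocol says of the normal-hearing listeners that "they are not fit with hearing aids and undergo fewer conditions".

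**The concern.** Two effect sizes stand in adjacent sentences and only one has a scale. G*Power's ANOVA routines work in Cohen's f, while the anticipated effect is in np2, so 0.23 could be either. The two are far apart: f = 0.23 is np2 = 0.050, and np2 = 0.23 is f = 0.547. The test, number of levels or groups, correlation and resulting N are also missing, and one power figure stands beside two group sizes whose listeners do not undergo the same conditions.

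Tuning status adds to this. The plan does not say whether it is a class of listeners or, as the Aim 2 wording on whether "restoring access to spectral information supports speech recognition in background noise" may suggest, a condition applied within each listener. If it is a class and 0.23 is f, the 40 would be well short of 80% for that factor, and a null result on it could be misread as evidence of no effect. Power is the only quantitative support offered for enrolment, so the question is a fair one.

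**Working it through.** **Inputs from the plan.** N = 20 and 40; power 80%; alpha 0.05; expected np2 = 0.37; sizing effect 0.23, scale not given.

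**Assumptions made here.** Two levels or two equal groups; sphericity holds; correlation rho = 0.5 unless varied. Calculations use the noncentral F distribution.

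**Scale conversion.** f² = np2/(1 − np2).
- np2 = 0.23: f² = 0.23/0.77 = 0.2987, f = 0.547.
- f = 0.23: f² = 0.0529, np2 = 0.0529/1.0529 = 0.050.
- np2 = 0.37: f² = 0.37/0.63 = 0.587, f = 0.766.

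**Noncentrality, with m measures per listener.**
- Within listeners: λ = N·m·f²/(1 − rho), on m − 1 and (N − 1)(m − 1) df.
- Within listeners, G*Power's as-in-SPSS option: λ = (N − 1)(m − 1)·f², same df.
- Between two groups: λ = N·m·f²/(1 + (m − 1)·rho), on 1 and N − 2 df.

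**The plan's own figure.** It cannot be reproduced as a single number, because the inputs are not given. What can be asked is whether 80% is attainable at 40 under each reading.

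*0.23 read as np2, N = 40*
- Within, two levels, rho 0.5: λ = 40 × 2 × 0.2987/0.5 = 47.8, power above 99.9%; N for 80% is 9.
- Within, as-in-SPSS option: λ = 39 × 0.2987 = 11.6, power 91.4%; N for 80% is 30.
- Two groups, one measure: λ = 40 × 0.2987 = 11.9, power 92.0%; N for 80% is 29.
- Two groups, two measures (the two dynamic-range levels), rho 0.5: λ = 40 × 2 × 0.2987/1.5 = 15.9, power 97%.

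*0.23 read as f, N = 40*
- Within, two levels, rho 0.5: λ = 40 × 2 × 0.0529/0.5 = 8.46, power 81.0%; N for 80% is exactly 40.
- The same at other correlations: power 52% at rho 0 and 96% at rho 0.7; N for 80% is 77 at rho 0, 54 at 0.3 and 25 at 0.7.
- Within, as-in-SPSS option: λ = 39 × 0.0529 = 2.06, power 29%; N for 80% is 152.
- Two groups, one measure: λ = 40 × 0.0529 = 2.12, power 29%; N for 80% is 151.
- Two groups, two measures, rho 0.5: λ = 40 × 2 × 0.0529/1.5 = 2.82, power 37%.

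*Expected effect, np2 = 0.37, N = 40*
- Two equal groups, one measure: λ = 40 × 0.587 = 23.5, power 99.7%.

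**The 20 normal-hearing listeners.** For a two-level within-listener test, power would be 99.6% (np2, rho 0.5), 62% (np2, as-in-SPSS option) or 50% (f, rho 0.5). These figures carry little weight. The listeners are not fitted with hearing aids, so they cannot enter the aided-setting comparisons of Aim 1, and the plan does not claim 80% power within the 20 for such a test.

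**Can the inputs be recovered from the 40?** No. Using f with two within-listener levels and rho 0.5 returns 40. Using np2 with a four-group test on 3 df returns 41 (power 79.2% at 40). Incompatible set-ups reach nearly the same N, so the stated 80% is neither confirmed nor refuted.

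**The case for a change.** The strongest argument for acting is that a power statement should be checkable and this one is not. The f reading is not fanciful, since it returns exactly 40 under an ordinary repeated-measures set-up. Under that same reading, a between-listener tuning factor has only 29% to 37% power. Even if np2 is accepted, the test and the N remain unstated. Two or three sentences from the sponsor's calculation record would settle it.

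The facts in that argument stand: the inputs are missing and the statement cannot be audited. What does not follow is a change to the plan. The low figures for the tuning factor need three assumptions together: that 0.23 is f, that tuning status divides listeners, and that the split is equal. The plan states none of them. Context leans towards np2, because the preceding sentence has just used that label and 0.23 then makes sense as a cautious value below 0.37. A null result would in any case be read from its estimate and confidence interval, not from the planned power. Whether tuning status is between or within listeners is a separate matter of describing the design, which the analyst will know from how the data are collected.

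**Conclusion.** The observation is correct but minor: 0.23 has no scale, test or resulting N, and the plan does not say whether the calculation sizes the 20, the 40 or both. No arithmetic error is shown. At 40 listeners the stated 80% is exceeded in every two-level or two-group case if 0.23 is np2 (91% or more), and is just met if it is f with two within-listener levels and rho 0.5 (81%). It is missed if 0.23 is f and the correlation is low (52% at rho 0), the as-in-SPSS option was used (29%), or tuning status forms two equal classes of listeners (29% with one measure, 37% with two at rho 0.5). Nothing in the plan establishes any of these. The effect the sponsor actually expects, np2 = 0.37, has 99.7% power for two equal groups in 40.

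Recording the inputs would help a reader but would leave enrolment, the comparisons and the models as they are. This is missing detail that the sponsor can supply from its own calculation, and the plan does not need to change. The conclusion rests on two levels or two equal groups, sphericity and the correlations shown.
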